7.2.2 Reporting of Pregnancy and Lactation to the Sponsor

Although pregnancy and lactation are not considered adverse events, it is the responsibility of investigators or their designees to report any pregnancy or lactation in a subject (spontaneously reported to them) that occurs during the trial.

Pregnancies and lactations that occur after the consent form is signed but before treatment allocation/randomization must be reported by the investigator if they cause the subject to be excluded from the trial, or are the result of a protocol-specified intervention, including but not limited to washout or discontinuation of usual therapy, diet, placebo treatment or a procedure. Pregnancies and lactations that occur from the time of treatment allocation/randomization through 14 days following cessation of Sponsor’s product must be reported by the investigator. All reported pregnancies must be followed to the completion/termination of the pregnancy. Pregnancy outcomes of spontaneous abortion, missed abortion, benign hydatidiform mole, blighted ovum, fetal death, intrauterine death, miscarriage and stillbirth must be reported as serious events (Important Medical Events). If the pregnancy continues to term, the outcome (health of infant) must also be reported.

Such events must be reported within 24 hours to the Sponsor either by electronic media or paper. Electronic reporting procedures can be found in the EDC data entry guidelines. Paper reporting procedures can be found in the Investigator Trial File Binder (or equivalent).

7.2.3 Immediate Reporting of Adverse Events to the Sponsor

7.2.3.1 Serious Adverse Events

A serious adverse event is any adverse event occurring at any dose or during any use of Sponsor's product that:

- Results in death;
- Is life threatening;
- Results in persistent or significant disability/incapacity;
- Results in or prolongs an existing inpatient hospitalization;
- Is a congenital anomaly/birth defect;
- Is an other important medical event.

Note: In addition to the above criteria, adverse events meeting either of the below criteria, although not serious per ICH definition, are reportable to the Sponsor in the same timeframe as SAEs to meet certain local requirements. Therefore, these events are considered serious by the Sponsor for collection purposes.

- Is a cancer;
- Is associated with an overdose.

Refer to [Table 13](#) for additional details regarding each of the above criteria.

For the time period beginning when the consent form is signed until treatment allocation/randomization, any serious adverse event, or follow up to a serious adverse event, including death due to any cause, that occurs to any subject must be reported within 24 hours to the Sponsor if it causes the subject to be excluded from the trial, or is the result of a protocol-specified intervention, including but not limited to washout or discontinuation of usual therapy, diet, placebo treatment or a procedure.

For the time period beginning at treatment allocation/randomization through 14 days following cessation of treatment, any serious adverse event, or follow up to a serious adverse event, including death due to any cause, whether or not related to the Sponsor's product, must be reported within 24 hours to the Sponsor either by electronic media or paper. Electronic reporting procedures can be found in the EDC data entry guidelines. Paper reporting procedures can be found in the Investigator Trial File Binder (or equivalent).

Additionally, any serious adverse event, considered by an investigator who is a qualified physician to be related to the Sponsor's product that is brought to the attention of the investigator at any time outside of the time period specified in the previous paragraph also must be reported immediately to the Sponsor.

All subjects with serious adverse events must be followed up for outcome.

7.2.3.2 Events of Clinical Interest

Selected non-serious and serious adverse events are also known as Events of Clinical Interest (ECI) and must be reported to the Sponsor.

For the time period beginning when the consent form is signed until treatment allocation/randomization, any ECI, or follow up to an ECI, that occurs to any subject must be reported within 24 hours to the Sponsor if it causes the subject to be excluded from the trial, or is the result of a protocol-specified intervention, including but not limited to washout or discontinuation of usual therapy, diet, placebo treatment or a procedure.

For the time period beginning at treatment allocation/randomization through 14 days following cessation of treatment, any ECI, or follow up to an ECI, whether or not related to the Sponsor's product, must be reported within 24 hours to the Sponsor, either by electronic

media or paper. Electronic reporting procedures can be found in the EDC data entry guidelines. Paper reporting procedures can be found in the Investigator Trial File Binder (or equivalent).

Events of clinical interest for this trial include:

1. an overdose of Sponsor's product, as defined in Section 7.2.1 - Definition of an Overdose for This Protocol and Reporting of Overdose to the Sponsor, that is not associated with clinical symptoms or abnormal laboratory results.
2. an elevated AST or ALT lab value that is greater than or equal to 3X the upper limit of normal and an elevated total bilirubin lab value that is greater than or equal to 2X the upper limit of normal and, at the same time, an alkaline phosphatase lab value that is less than 2X the upper limit of normal, as determined by way of protocol-specified laboratory testing or unscheduled laboratory testing.*

*Note: These criteria are based upon available regulatory guidance documents. The purpose of the criteria is to specify a threshold of abnormal hepatic tests that must trigger an additional evaluation for an underlying etiology. The trial site guidance for assessment and follow up of these criteria can be found in the Investigator Trial File Binder (or equivalent).

It may also be appropriate to conduct additional evaluation for an underlying etiology in the setting of abnormalities of liver blood tests including AST, ALT, bilirubin, and alkaline phosphatase that do not meet the criteria noted above. In these cases, the decision to proceed with additional evaluation will be made through consultation between the study investigators and the Sponsor Clinical Director. However, abnormalities of liver blood tests that do not meet the criteria noted above are not ECIs for this trial.

7.2.3.3 Protocol-Specific Exceptions to Serious Adverse Event Reporting

7.2.4 Evaluating Adverse Events

An investigator who is a qualified physician will evaluate all adverse events with respect to the elements outlined in [Table 13](#). The investigator's assessment of causality is required for each adverse event. Refer to [Table 13](#) for instructions in evaluating adverse events.

Table 13 Evaluating Adverse Events

Maximum Intensity	Mild	awareness of sign or symptom, but easily tolerated (for pediatric trials, awareness of symptom, but easily tolerated)
	Moderate	discomfort enough to cause interference with usual activity (for pediatric trials, definitely acting like something is wrong)
	Severe	incapacitating with inability to work or do usual activity (for pediatric trials, extremely distressed or unable to do usual activities)
Seriousness	A serious adverse event (AE) is any adverse event occurring at any dose or during any use of Sponsor's product that:	
	† Results in death ; or	
	† Is life threatening ; or places the subject, in the view of the investigator, at immediate risk of death from the event as it occurred [Note: This does not include an adverse event that, had it occurred in a more severe form, might have caused death.]; or	
	† Results in a persistent or significant disability/incapacity (substantial disruption of one's ability to conduct normal life functions); or	
	† Results in or prolongs an existing inpatient hospitalization (hospitalization is defined as an inpatient admission, regardless of length of stay, even if the hospitalization is a precautionary measure for continued observation. (Note: Hospitalization for an elective procedure to treat a pre-existing condition that has not worsened is not a serious adverse event. A pre-existing condition is a clinical condition that is diagnosed prior to the use of a Merck product and is documented in the patient's medical history.); or	
	† Is a congenital anomaly/birth defect (in offspring of subject taking the product regardless of time to diagnosis); or	
	Is a cancer (although not serious per ICH definition, is reportable to the Sponsor within 24 hours to meet certain local requirements); or	
	Is associated with an overdose (whether accidental or intentional). Any adverse event associated with an overdose is considered a serious adverse event for collection purposes. An overdose that is not associated with an adverse event is considered a non-serious event of clinical interest and must be reported within 24 hours.	
Other important medical events that may not result in death, not be life threatening, or not require hospitalization may be considered a serious adverse event when, based upon appropriate medical judgment, the event may jeopardize the subject and may require medical or surgical intervention to prevent one of the outcomes listed previously (designated above by a †).		
Duration	Record the start and stop dates of the adverse event. If less than 1 day, indicate the appropriate length of time and units	
Action taken	Did the adverse event cause the Sponsor's product to be discontinued?	
Relationship to Sponsor's Product	Did the Sponsor's product cause the adverse event? The determination of the likelihood that the Sponsor's product caused the adverse event will be provided by an investigator who is a qualified physician. The investigator's signed/dated initials on the source document or worksheet that supports the causality noted on the AE form, ensures that a medically qualified assessment of causality was done. This initialed document must be retained for the required regulatory time frame. The criteria below are intended as reference guidelines to assist the investigator in assessing the likelihood of a relationship between the test drug and the adverse event based upon the available information	
	The following components are to be used to assess the relationship between the Sponsor's product and the AE ; the greater the correlation with the components and their respective elements (in number and/or intensity), the more likely the Sponsor's product caused the adverse event:	
	Exposure	Is there evidence that the subject was actually exposed to the Sponsor's product such as: reliable history, acceptable compliance assessment (pill count, diary, etc.), expected pharmacologic effect, or measurement of drug/metabolite in bodily specimen?
	Time Course	Did the AE follow in a reasonable temporal sequence from administration of the Sponsor's product? Is the time of onset of the AE compatible with a drug-induced effect (applies to trials with investigational medicinal product)?
	Likely Cause	Is the AE not reasonably explained by another etiology such as underlying disease, other drug(s)/vaccine(s), or other host or environmental factors

Relationship to Sponsor's Product (continued)	The following components are to be used to assess the relationship between the Sponsor's product and the AE: (continued)	
	Dechallenge	Was the Sponsor's product discontinued or dose/exposure/frequency reduced? If yes, did the AE resolve or improve? If yes, this is a positive dechallenge. If no, this is a negative dechallenge. (Note: This criterion is not applicable if: (1) the AE resulted in death or permanent disability; (2) the AE resolved/improved despite continuation of the Sponsor's product; (3) the trial is a single-dose drug trial); or (4) Sponsor's product(s) is/are only used one time.)
	Rechallenge	Was the subject re-exposed to the Sponsor's product in this trial? If yes, did the AE recur or worsen? If yes, this is a positive rechallenge. If no, this is a negative rechallenge. (Note: This criterion is not applicable if: (1) the initial AE resulted in death or permanent disability, or (2) the trial is a single-dose drug trial); or (3) Sponsor's product(s) is/are used only one time.) NOTE: IF A RECHALLENGE IS PLANNED FOR AN ADVERSE EVENT WHICH WAS SERIOUS AND WHICH MAY HAVE BEEN CAUSED BY THE SPONSOR'S PRODUCT, OR IF RE-EXPOSURE TO THE SPONSOR'S PRODUCT POSES ADDITIONAL POTENTIAL SIGNIFICANT RISK TO THE SUBJECT THEN THE RECHALLENGE MUST BE APPROVED IN ADVANCE BY THE SPONSOR CLINICAL DIRECTOR AND THE INSTITUTIONAL REVIEW BOARD/INDEPENDENT ETHICS COMMITTEE.
	Consistency with Trial Treatment Profile	Is the clinical/pathological presentation of the AE consistent with previous knowledge regarding the Sponsor's product or drug class pharmacology or toxicology?
The assessment of relationship will be reported on the case report forms /worksheets by an investigator who is a qualified physician according to his/her best clinical judgment, including consideration of the above elements.		
Record one of the following:		Use the following scale of criteria as guidance (not all criteria must be present to be indicative of a Sponsor's product relationship).
Yes, there is a reasonable possibility of Sponsor's product relationship.		There is evidence of exposure to the Sponsor's product. The temporal sequence of the AE onset relative to the administration of the Sponsor's product is reasonable. The AE is more likely explained by the Sponsor's product than by another cause.
No, there is not a reasonable possibility of Sponsor's product relationship		Subject did not receive the Sponsor's product OR temporal sequence of the AE onset relative to administration of the Sponsor's product is not reasonable OR the AE is more likely explained by another cause than the Sponsor's product. (Also entered for a subject with overdose without an associated AE.)

7.2.5 Sponsor Responsibility for Reporting Adverse Events

All Adverse Events will be reported to regulatory authorities, IRB/IECs and investigators in accordance with all applicable global laws and regulations, i.e., per ICH Topic E6 (R1) Guidelines for Good Clinical Practice.

8.0 STATISTICAL ANALYSIS PLAN

8.1 Statistical Analysis Plan Summary

This section contains a brief summary of the statistical analyses for this trial. Full detail is in the Statistical Analysis Plan (SAP) (Section 8.2).

Statistical Methods

Primary Objective (Safety): Incidence of adverse experiences will be descriptively summarized. Summary statistics and plots will be generated for the change from baseline values in the vital signs, ECG parameters, and selected laboratory safety parameters for subjects, as deemed clinically appropriate. Depending on the safety parameter, the difference from baseline will either be computed on the original scale (raw change from baseline) or on the log scale and back-transformed for reporting (percent change from baseline). Summary statistics for the raw laboratory safety tests, ECGs, and/or vital signs may also be computed, as deemed clinically appropriate.

Primary Objective (Pharmacodynamics): The log₁₀ plasma HIV-RNA (copies/mL) measurements from subjects in all panels will be pooled and analyzed based on a longitudinal data analysis model containing fixed effects for dose level, time (pre-dose, 168 hrs post-dose) and dose level by time interaction, and a random effect for patient. The change from baseline for each dose level at 168 hours post-baseline will be estimated from this model. A posterior distribution for the true mean change from baseline at 168 hours will be generated for each dose level using flat priors under a normal likelihood assumption. Historical placebo data from recent monotherapy studies in HIV-1 subjects (MK-0518 Protocol 004, MK-1439 Protocol 005, MK-6186 Protocol 007, and MK-1972 Protocol 003) will be separately analyzed based on a longitudinal data analysis model containing fixed effects for study and time (pre-dose, 168 hours post-dose), and a random effect for patient. The change from baseline for placebo at 168 hours post-baseline will be estimated from this model, and a posterior distribution for the true mean change from baseline at 168 hours will be generated using flat priors under a normal likelihood assumption. Using the posterior distributions for each dose level and placebo, the posterior distribution of the true mean difference between each dose level and placebo will be generated, and the posterior probability that the true mean difference in the log₁₀ plasma HIV-1 RNA reduction from baseline between MK-4250 and placebo is at least 1.4 log₁₀ copies/mL will be calculated. An 80% posterior probability for at least one dose level that also exhibits an acceptable safety and tolerability profile will satisfy the primary pharmacodynamics hypothesis.

Power

If the true SD of the log₁₀ reduction from baseline in plasma HIV-RNA at 168 hours postdose is 0.2 (0.3), there is ~80% power to yield at least 80% posterior probability that the

true mean difference in the plasma HIV-1 RNA reduction from baseline between MK-4250 and placebo is at least 1.4 log₁₀ copies/mL, if the true mean log₁₀ reduction is at least 1.56 log₁₀ (1.63 log₁₀) with N=6 for MK-4250 in a panel and N=20 historical placebo subjects. The SD values of 0.2 and 0.3 are chosen based on a SD of 0.26 observed for Day 8 change from baseline in log₁₀ HIV RNA for 400 mg BID raltegravir.

8.2 Statistical Analysis Plan

The statistical analysis of the data obtained from this study will be conducted by, or under the direct auspices of, the Early Clinical Development Statistics Department in collaboration with the Quantitative Pharmacology and Pharmacometrics Department and Translational Pharmacology Department of the Sponsor.

If, after the study has begun, changes are made to the statistical analysis plan stated below, then these deviations to the plan will be listed, along with an explanation as to why they occurred, in the Clinical Study Report.

8.2.1 Hypotheses

Primary Pharmacodynamics Hypothesis: At a dose that is sufficiently safe and generally well tolerated, MK-4250 has superior antiretroviral activity compared to placebo, as measured by change from baseline in plasma HIV-1 RNA (log₁₀ copies/mL) at 168 hours postdose. That is, the true mean difference in the plasma HIV-1 RNA reduction from baseline between MK-4250 and placebo is at least 1.4 log₁₀ copies/mL.

Secondary Pharmacokinetic Hypothesis: The true geometric mean C_{168hr} is > 1250 nM following single dose administration of MK-4250 for at least one dose level of MK-4250.

8.2.2 Analysis Endpoints

Primary Endpoints

Safety: Primary safety endpoints will include all types of adverse experiences, in addition to laboratory safety tests, ECGs, and vital signs.

Pharmacodynamics: The primary pharmacodynamics variables in this study include plasma HIV-1 RNA pre-dose and at the time points listed in the Study Flow Chart up until the time at which ART is initiated.

Secondary Endpoints

The secondary endpoints in this study include: MK-4250 plasma AUC_{0-last}, AUC_{0-inf}, AUC_{0-168hr}, T_{max}, C_{max}, C_{168hr}, t_{1/2}, CL/F and V_z/F.

8.2.3 Approaches to Analyses

The following populations are defined for the analysis and reporting of data. All subjects will be reported, and their data analyzed, according to the treatment(s) they actually received.

All Subjects as Treated (ASaT): The All Subjects as Treated Population consists of all subjects who received at least one dose of treatment. This population will be used for assessments of safety and tolerability.

Per-Protocol (PP): The Per-Protocol Population consists of the subset of subjects who comply with the protocol sufficiently to ensure that generated data will be likely to exhibit the effects of treatment, according to the underlying scientific model. Compliance covers such considerations as exposure to treatment, availability of measurements and absence of major protocol deviations. Major protocol deviations will be identified to the extent possible by individuals responsible for data collection/compliance, and its analysis and interpretation. Any subjects or data values excluded from analysis will be identified, along with their reason for exclusion, in the CSR. At the end of the study, all subjects who are compliant with the study procedure as aforementioned and have available data from at least one treatment will be included in the Per-Protocol dataset. This population will be used for the PK and PD analyses.

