This was a randomized, alternating panel, placebo-controlled, double-blind trial evaluating the safety and pharmacokinetics of single rising doses of MK-4250 in 40 healthy male subjects. Single oral doses of 20 to 1600 mg capsule formulation and 100 to 1200 mg tablet formulation were administered. Food effect was also evaluated at 400 mg for both formulations. MK-4250 was generally well tolerated, the most common AEs (≥ 2 incidents) reported by subjects administered MK-4250 were headache, abdominal discomfort, and dizziness. All AEs were mild or moderate in intensity and transient in nature. There were no SAEs and no discontinuations due to an AE. There were no clinically meaningful changes in ECGs, vital signs and laboratory safety evaluations.

Protocol 002 (Panels A and B)

As of 21-Jun-2018, 12 HIV-infected male subjects have been administered (fasted) single oral doses of MK-4250 (6 received 150 mg in Panel A and 6 received 600 mg in Panel B). Panel A and B are clinically complete. Preliminary PK, viral load and safety data are provided. Exposure of MK-4250 in HIV-infected subjects has been, on average, lower than that observed in uninfected subjects (Table 2). In addition, PK variability has been higher with some subjects exhibiting PK comparable to uninfected subjects while others exhibit diminished absorption and/or shorter $t_{1/2}$ resulting in lower than anticipated C_{168hr}.

Following the 150 mg dose, the mean (range) change from baseline in viral load was -1.56 (-1.21 to -1.89) log₁₀ copies/mL. Following the 600 mg dose, the mean (range) change from baseline in viral load at 7 days post-dose was -1.76 (-1.06, -2.27) log₁₀ copies/mL. This change is comparable to the mean change observed in monotherapy studies following 7 days of dosing for other InSTIs (see Section 4.2.2).

Table 2 Preliminary Geometric Mean (% Coefficient of Variation) MK-4250 Plasma Pharmacokinetics Following Single Dose Administration of MK-4250 to HIV-1 Infected Subjects (N=6 per Dose)

Dose (mg)	C _{max} (μM)	T _{max} ¹ (hr)	t _{1/2} (hr)	AUC _{0-∞} (μM·hr)	AUC _{0-last} (μM·hr)	AUC ₀₋₁₆₈ (μM·hr)	C ₁₆₈ (μM)	CL _F (L/hr)	V _F (L)
150	16.6 (46.7)	4.00 (1.00 - 4.00)	35.9 (22.9)	785 (54.6)	774 (54)	751 (52.6)	0.558 (117)	0.456 (54.6)	23.6 (45.1)
600	37.6 (26)	4.00 (4.00 - 6.00)	38.5 (31.9)	2120 (18.4)	2040 (17.1)	1980 (16.7)	2.2 (57.4)	0.676 (18.4)	37.6 (23.5)

¹Median (Min-Max)

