As described in Section 4.1.3, exposure of MK-4250 in HIV-infected subjects was on average lower and more variable compared to healthy subjects. Although viral load reduction was achieved in both Panels A and B, the increased variability led to some subjects having C168hr well below the PK target. As viral load reduction and C168hr were generally correlated, a portion of subjects with lower C168hr also appeared to have sub-maximal virologic response. The results of Panel A and B support the omission of Panel C as submaximal viral load response was observed in some subjects and the conduct of Panel D at a dose of 900 mg, fasted. In addition, the protocol is being amended to include Panel E at a dose up to 900 mg with a low fat meal and Panel F at a dose up to 900 mg with a moderate fat meal. As MK-4250 exposures increase less than dose proportionally, dosing with food allows for further increases in exposure to further explore the dose- and exposure-response relationship of MK-4250. Additional PK and safety data are available and demonstrate doses up to 1200 mg to be generally well-tolerated, supporting conduct of Panel D at 900 mg.

Panel E Dose Selection

The dose for Panel E will be selected once safety and VL data (from at least 7 days post dose) obtained from Panel D have been reviewed. This dose will be selected to gain further clarity on the exposure-VL relationship and/or to explore the safety, PK and VL effects at higher exposures of MK-4250. The selected dose for Panel E will not exceed 900 mg of tablet formulation. This dose will be administered with a low fat meal in order to further boost exposures above those achieved with 900 mg, fasted. [Table 5](#) shows the predicted PK parameter values for a 900 mg dose of MK-4250 with food in an HIV-infected population. These projections were made using a Population PK model including healthy subject data from Protocols 001 and 003 and HIV-infected subject data from Protocol 002 Panels A and B. The effect of a low fat meal is anticipated to be similar to that observed in uninfected subjects in Protocol 003. The projected AUC_{0-168hr} in Panel E does not exceed that obtained following a single 1200 mg, fasted dose of MK-4250 shown to be generally well tolerated in Protocol 001.

Table 5 Observed Geometric Mean (%Coefficient of Variation) MK-4250 Plasma PK and for Population Pharmacokinetic Model Predicted 50th Percentile MK-4250 PK for Panels E and F

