7.1.1.8 Trial Compliance (Medication/Diet/Activity/Other)

Administration of trial medication will be witnessed by the investigator and/or trial staff.

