Individual values will be listed for each PK parameter by treatment, and the following (non-model-based) descriptive statistics will be provided: N (number of subjects with non-missing data), arithmetic mean, standard deviation, arithmetic percent CV (calculated as 100 x standard deviation/arithmetic mean), median, minimum, maximum, geometric mean, and geometric percent CV (calculated as 100 x sqrt(exp(s²) - 1), where s² is the observed variance on the natural log-scale).

Exploratory (Pharmacokinetic/Pharmacodynamic)

The pharmacokinetic-pharmacodynamic and dose-pharmacodynamic association of MK-4250 will be explored. Graphs to visualize the association of the Day 7 reduction in log₁₀ plasma HIV-1 RNA levels with MK-4250 C_{168hr} plasma concentration and dose will be generated. Exposure levels and doses that result in various proportions of the population (e.g., 80%, 90%) that have at least 1.4 log₁₀ reduction from baseline in plasma HIV-1 RNA levels with high confidence may be estimated.

General

For all analyses, data will be examined for departures from the assumptions of the statistical model(s) as appropriate; e.g., heteroscedasticity, nonnormality of the error terms.

Distribution-free methods may be used if a serious departure from the assumptions of the model(s) is observed, or suitable data transformations may be applied.

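### Does limiting the viral-load and C168hr analyses to a loosely defined Per-Protocol set put the hypothesis results at risk?

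*Combined protocol and SAP*

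**What the plan says.** Section 8.2.3 defines two populations. The all-treated set (ASaT) has one use: "This population will be used for assessments of safety and tolerability". For the Per-Protocol set the section states: "This population will be used for the PK and PD analyses". Both hypothesis analyses in section 8.2.4 (viral load at 168 hours and geometric mean C168hr) therefore rest on Per-Protocol.

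Membership depends on sufficient compliance with the protocol: "Compliance covers such considerations as exposure to treatment, availability of measurements and absence of major protocol deviations". On who decides, it says: "Major protocol deviations will be identified to the extent possible by individuals responsible for data collection/compliance, and its analysis and interpretation". The section adds three things. Excluded subjects or values, with reasons, are reported in the Clinical Study Report. The set is formed when the study ends. At that point, all subjects who complied with the procedures and have data from at least one treatment are included.

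Section 7.1.1.8 bears on compliance: "Administration of trial medication will be witnessed by the investigator and/or trial staff".

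**The concern.** The grounds for exclusion are illustrative. Exposure to treatment is not defined, major deviations are not listed, and nothing says that a low concentration or a weak response is no reason to drop a subject. The trial is open-label (section 5.2.3), viral-load data are reviewed between panels, and the people who identify deviations include those who interpret the results.

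The background sections make this more than a formality. Section 4.1.3.1 reports that "PK variability has been higher with some subjects exhibiting PK comparable to uninfected subjects while others exhibit diminished absorption", and section 4.2.2 that "a portion of subjects with lower C168hr also appeared to have sub-maximal virologic response". If exposure were read as measured drug level, an exclusion would be tied to outcome. The per-dose estimates and the optional exposure-response work in section 8.2.4 would then look better than the drug's effect in all dosed subjects. Reporting exclusions discloses this but does not prevent it.

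**Working it through.** **1. The plan's own figure.** With flat priors, a normal likelihood and known SD, the 80% posterior rule is a one-sided z-test of a difference above 1.4 at level 0.20. Inputs from section 8.2.6: N = 6 against N = 20; SD 0.2 with true mean 1.56, or SD 0.3 with true mean 1.63. Placebo change is assumed to be 0.
- SE = SD × √(1/6 + 1/20) = 0.4655 × SD, which gives 0.0931 and 0.1396.
- Power = Φ((mean − 1.4)/SE − 0.8416) = 81.0% and 79.0%. The stated figure of about 80% reproduces.
- The observed margin above 1.4 needed to pass is 0.8416 × SE = 0.078 and 0.118.

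**2. What one outcome-driven exclusion could do.** Section 4.1.3.1 gives mean reductions (range) of 1.56 (1.21 to 1.89) in Panel A and 1.76 (1.06 to 2.27) in Panel B, N = 6 each. The Panel A figure has no stated time and is taken as 168 hours. Removing the weakest responder gives:
- A: (6 × 1.56 − 1.21)/5 = 1.63, a rise of 0.07.
- B: (6 × 1.76 − 1.06)/5 = 1.90, a rise of 0.14.

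With the true mean exactly at threshold, simulation shows that removing the lowest of six raises the chance of passing from 20% to about 36% for viral load and from 30% to about 52% for C168hr (known SD). These are upper bounds, because they assume the exclusion falls on the weakest value.

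**3. Whether the verdicts need any exclusion.** Section 8.2.4 pools all panels in one model and specifies no panel-specific variance, so a pooled SD is the right one.
- SDs compatible with six values and the reported mean, minimum and maximum: A 0.215 to 0.362; B 0.390 to 0.596.
- Pooled, lower end: √((0.215² + 0.390²)/2) = 0.315. Upper end: √((0.362² + 0.596²)/2) = 0.493.
- Posterior = Φ((mean − 1.4)/(0.4655 × SD)), with placebo change 0, N = 20 and the same SD.

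| | SD 0.315 | SD 0.493 |
|---|---|---|
| Panel A, six kept | Φ(0.16/0.147) = 0.86 | Φ(0.16/0.230) = 0.76 |
| Panel B, six kept | Φ(0.36/0.147) = 0.99 | Φ(0.36/0.230) = 0.94 |

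If Panel A lost its weakest responder and the SD stayed the same, SE would be SD × √(1/5 + 1/20) = 0.5 × SD. The posterior would be Φ(0.23/0.157) = 0.93 or Φ(0.23/0.247) = 0.82. So one exclusion could carry Panel A alone across 80%, but the criterion needs only one dose level and Panel B meets it with all six.

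For C168hr, Table 2 gives geometric means of 0.558 and 2.2 µM with CVs of 117% and 57.4%, read here as geometric.
- Log-SD = √ln(1 + CV²) = 0.929 (A) and 0.534 (B); pooled √((0.929² + 0.534²)/2) = 0.757.
- Panel B: ln(2.2/1.25)/(0.757/√6) = 1.83, so the posterior is 0.966 (normal) or 0.951 (t, 10 df), against the 70% required.
- Panel A: the lowest of six lies at most 5/√6 = 2.04 SDs below the mean, so dropping it gives at most 0.558 × exp(2.04 × 0.929/5) = 0.82 µM, still below 1.25.

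**4. Whether the wording permits the exclusion.** Exposure to treatment is listed as an aspect of compliance. A subject who swallowed a witnessed dose has complied, however much was absorbed. The inclusion sentence then requires that subject to be in the set if data exist. The preliminary summaries agree with this reading: Table 2 keeps all six subjects at each dose, although the same section describes poor absorption in some of them.

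**The case for a change.** The best case for a change is that it is cheap. Two or three sentences and one extra model run per hypothesis would define exposure as the dose having been taken, bar exclusion for low concentration or weak response, and place an all-treated result beside the Per-Protocol one. If the sponsor never intended such exclusions, it loses nothing and the result is harder to challenge. Panels D to F are still to come, and the per-dose estimates will inform later dose selection.

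It is true that section 8.2.3 contains no explicit prohibition, and that an improper exclusion could move a single panel's estimate, as Panel A shows. But the harm requires analysts to act against the inclusion sentence, and nothing in the documents suggests that they would. An exclusion would also be easy to see: reasons go in the study report, section 8.2.4 plans individual viral-load plots and individual PK listings, and Panels A and B are already on record with six subjects each. With a single witnessed dose, the all-treated run would use almost the same subjects as the planned one.

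**Conclusion.** No change is needed. Section 8.2.3 leaves a gap in definition that analysts would fill sensibly, since its compliance basis and inclusion rule keep in any dosed subject with data. Using Per-Protocol for PK and PD is a defensible choice in a single-dose Phase Ib study.

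The potential effect of misuse is real but bounded: at most 0.07 and 0.14 log10 on the Panel A and B means. With all six kept, Panel B satisfies the viral-load criterion (0.94 to 0.99 against 80%) and the C168hr criterion (about 0.95 to 0.97 against 70%), so no verdict that needs only one dose level is shown to depend on an exclusion. Panel A alone is not certain to pass (0.76 to 0.86).

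These figures assume zero placebo change, 20 placebo subjects, a common SD pooled over Panels A and B only, geometric CVs, and an acceptable safety profile at the Panel B dose. Later panels would alter the pooled SD. A sentence saying that exposure means the dose was taken would be a harmless clarification, but the soundness of the analysis does not depend on it.
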